12.5 Subgroup Analyses

Subgroup analyses are planned for exploratory purposes; p-values will be presented as descriptive statistics. Subgroup analyses will be performed for the primary and key secondary efficacy endpoint 1 using the Full Analysis Set, and for the analysis of safety endpoints (AEs) using the Safety Set. Data will be summarized by treatment within subgroup.

12.5.1 Age Group

A subgroup analysis of age will be conducted using 18 years and 64 years as cut points to examine the treatment effect in adolescent vs. adult subjects.

- <18 years
- 18-64 years
- >= 65 years

12.5.2 Sex

A subgroup analysis will be conducted to examine the treatment effect in male vs. female subjects.

- Male
- Female

12.5.3 Race Group

Subgroup analyses will be conducted by race to examine the treatment effect in White vs. those subjects of other races.

- White
- Other Races

12.5.4 Use of Prophylactic therapy with C1 INH at Randomization

Subgroup analyses will be conducted by prophylactic therapy with C1 INH at randomization (defined as taken within 5 days prior to randomization).

- Use of prophylactic therapy with C1 INH at randomization: Yes
- Use of prophylactic therapy with C1 INH at randomization: No

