4.2 Exclusion Criteria

Subjects are excluded from the study if any of the following exclusion criteria are met.

1. Adults (≥ 18 years of age) receiving prophylactic IV CINRYZE that exceeds the approved dosing regimen of 1000 U every 3 or 4 days (receiving a weekly dose > 2000 U).
2. Adolescents (≥ 12 and < 18 years of age) currently receiving prophylactic therapy with C1 INH (not applicable to Germany and Israel).
3. Have had signs or symptoms of an angioedema attack within 2 days prior to the first dose of the investigational product in Treatment Period 1.
4. Have received any C1 INH therapy or any blood product for the treatment or prevention of angioedema attacks within 3 calendar days prior to the first dose of investigational product in Treatment Period 1.
5. If female, have started or changed the dose of any hormonal contraceptive regimen or hormone replacement therapy (ie, estrogen/progestin containing products) within 2 months prior to the screening visit.
6. Have a history of hypercoagulability (abnormal blood clotting) or other predisposition for thromboembolism.
7. Have a diagnosis of acquired angioedema or known presence of anti-C1 INH antibodies.
8. Have a history of allergic reaction to C1 INH products, including CINRYZE (or any components of CINRYZE), other blood products, or Firazyr (icatibant).
9. Be pregnant or breastfeeding.

10. Have received an investigational drug within 30 days prior to the first dose of investigational product in Treatment Period 1.
11. Have, as determined by the investigator and/or the sponsor's medical monitor, any surgical or medical condition (including positive for hepatitis B, hepatitis C, or HIV infection; alcohol, drug, or medication abuse within 1 year before screening; or mental condition rendering the subject or parent(s)/legal guardian unable to understand the nature, scope of the study, and possible consequences of the study), or relationship to study staff or sponsor (including people accommodated in an institution as well as people who are dependent on the sponsor, CRO, site or the investigator) that could interfere with the administration of investigational product or interpretation of study results.

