6.3 Allocation of Subjects to Treatment Sequence

This is a double-blind, placebo-controlled, 2-period, 3-sequence, partial crossover study. At least 66 eligible subjects will be randomized to 1 of 3 treatment sequences (Table 7) prior to the first dose of investigational product in Treatment Period 1. The actual treatment sequence given to individual subjects is determined by a randomization schedule automatically assigned by the IRT.

Table 7 Treatment Sequences

Sequence	Treatment: Period 1/Period 2	Approximate Number of Subjects Randomized
1	A/B	26
2	B/A	26
3	A/A	14

Treatment A=2000 IU (4.0 mL) C1 esterase inhibitor [human] liquid for injection administered SC twice weekly (every 3 or 4 days) for 14 weeks.

Treatment B=Placebo (4.0 mL) administered SC twice weekly (every 3 or 4 days) for 14 weeks.

Subject numbers are assigned to all subjects as they consent to take part in the study. Within each level of use of prophylactic therapy with C1 INH across sites, the subject number is assigned to subjects according to the sequence of presentation for study participation. Subject number is unique within a protocol.

The randomization number represents a unique number corresponding to treatment sequence allocated to the subject, once eligibility has been determined. A randomization number will be assigned by the IRT at the baseline visit (predose Visit 1a) after subject eligibility has been confirmed using the randomization criteria. The randomization schedule will be stratified for use of prophylactic therapy with C1 INH at the time of enrollment versus no prophylactic therapy with C1 INH at the time of enrollment. Subjects will be randomized to the treatment sequence 1 (A/B), 2 (B/A), or 3 (A/A) in the randomization ratio of 2:2:1.

The subject's treatment sequence will be held in strict confidence. The treatment sequence for an individual subject may be broken in cases of emergency or for reasons of subject safety, as described in Section 6.4.1.

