7.2 Study Evaluations and Procedures

7.2.1 Demographic and Other Baseline Characteristics

Subject demographic details, medical history (including HAE history, Section 7.2.3.1), prior and concomitant medication data, vital signs, height, weight, physical examination, 12-lead ECG, biochemistry, hematology, coagulation, virology screening, and serum β -hCG pregnancy test will be collected at the time of enrollment at the Screening Visit.

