2.2 Randomization

The randomization schedule will be stratified for use of prophylactic therapy with C1 INH at the time of enrollment versus no prophylactic therapy with C1 INH at the time of enrollment. At least 66 eligible subjects will be randomized to 1 of 3 treatment sequences prior to the first dose of investigational product in Treatment Period 1. The actual treatment sequence given to individual subjects is determined by a randomization schedule automatically assigned by the IRT.

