10. EFFICACY ANALYSES

10.1 Primary Efficacy Variable(s) and Analysis

The primary efficacy analysis will be conducted over the subjects in the Full Analysis Set that are randomized to Treatment Sequence 1 (A/B) or 2 (B/A) to evaluate of the efficacy of SC administration of C1 esterase inhibitor [human] liquid for injection compared to placebo.

The primary efficacy endpoint is defined as the normalized number of angioedema attacks during a treatment period. The NNA is expressed as the number of attacks per month (ie, 30.4 days) of exposure:

NNA = 30.4 x (number of attacks during treatment period)/(days of treatment period)

If a subject discontinues during the treatment period, the denominator of the NNA will be the days on treatment for that subject; this is equivalent to the last observation carried forward imputation method to impute the missing information following the subject's discontinuation.

To test the hypothesis that the NNA of C1 esterase inhibitor [human] liquid for injection is greater than or equal to the NNA of placebo, and the alternative hypothesis that the NNA of C1 esterase inhibitor [human] liquid for injection is less than the NNA of placebo as below:

H_{0:} μ _{C1 INH} - μ placebo ≥ 0 VS H_{1:} μ _{C1 INH} - μ placebo < 0

A linear mixed effect model will be performed to analyze the primary efficacy endpoint with period, sequence, use of prophylactic therapy with C1 INH, which is derived by long-term prevention with C1 INH at randomization, and treatment as fixed effects, and subject nested within sequence as a random effect. If the variance-covariance matrix of random effects is not positive definite, a mixed effect model with the same fixed effects and subject nested within sequence as repeated measurements will be performed instead; the repeated measurement is equivalent to the random effect in terms of statistical testing and point estimates of coefficients of fixed effects, however, the variance covariance matrix of random effects will not be estimated. The mean treatment difference ($\mu_{C1 \text{ INH}} - \mu_{placebo}$) will be estimated with a 95% CI provided. The upper confidence bound of 95% CI must be less than 0 in order for C1 INH to be considered superior to the placebo.

A summary of NNA during each treatment period by treatment sequences will be provided for the Full Analysis Set.

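### The 5-day rule defining the C1 INH prophylaxis subgroup in SAP 12.5.4 does not match the randomization stratum, so some stratum members may be analysed as non-users

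*SAP*

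**What the plan says.** Four places bear on one baseline characteristic.

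- **Stratum.** Protocol 6.3: "The randomization schedule will be stratified for use of prophylactic therapy with C1 INH at the time of enrollment", against no such use. SAP 2.2 repeats this. Neither gives a day window. Protocol 7.2.1 links enrollment to screening, listing baseline data that "will be collected at the time of enrollment at the Screening Visit", and Protocol 7.1.1 allows screening up to 21 days before the first dose.
- **Subgroup.** SAP 12.5.4 uses "prophylactic therapy with C1 INH at randomization (defined as taken within 5 days prior to randomization". Under SAP 12.5 this split applies to the primary endpoint, key secondary endpoint 1 and adverse events. All subgroup analyses are exploratory, with descriptive p-values.
- **C1 INH-free interval.** Exclusion criterion 4 (Protocol 4.2) bars C1 INH for treatment or prevention "within 3 calendar days prior to the first dose of investigational product in Treatment Period 1". Protocol 6.3 puts randomization at the same visit: "A randomization number will be assigned by the IRT at the baseline visit (predose Visit 1a".
- **Model factor.** Protocol 9.8.1 puts the stratification factor in the primary model. SAP 10.1 instead specifies "use of prophylactic therapy with C1 INH, which is derived by long-term prevention with C1 INH at randomization", and SAP 10.4 does the same for the other secondary endpoints. SAP 16, on changes from the protocol, states that there are none.

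**The concern.** C1 INH prophylaxis is the only stratification factor, so readers will take the SAP 12.5.4 subgroup to be the randomized strata. Under the written rule, membership depends partly on how many days passed between the last prophylactic dose and Visit 1a. Two adults on the same regimen and in the same stratum can land in different subgroups because of visit scheduling. Exclusion criterion 3, which requires no attack signs or symptoms in the 2 days before the first dose, is one reason a visit might slip.

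The mixing matters because the two groups enter on different histories. Under inclusion criterion 3, C1 INH users qualify on their attack rate before starting prevention, and non-users on the three months before screening. Moving users into *No* blurs that distinction, and the groups so formed no longer carry the balance across sequences that stratification was meant to give.

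A second, separate inconsistency is that the model covariate is a derived status at randomization, although the protocol names the stratification factor.

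**Working it through.** The plan attaches no figure to the 5-day rule, so there is nothing to reproduce. The check is calendar arithmetic.

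**Inputs**

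- Day 0 is Visit 1a, with randomization and then the first dose (Protocol 6.3).
- The *Yes* window is Days -5 to -1 (SAP 12.5.4).
- The barred days are Days -3 to -1 (exclusion criterion 4). This is a minimum interval; no maximum is stated.
- The approved IV prophylaxis interval is every 3 or 4 days (exclusion criterion 1).
- Both windows are counted in whole calendar days ending the day before Visit 1a. This convention is an assumption.

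**Usable days**

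5 days in the window minus 3 barred days = 2 days. A compliant user is *Yes* with a last dose on Day -4 or -5 and *No* with a last dose on Day -6 or earlier.

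**Share of stratum members classed as *No***

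The documents give no last-dose distribution, so the share depends on an assumption.

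1. *Every last dose falls on Day -4 or -5.* Share = 0%.
2. *Visit 1a falls on a random day of the dosing cycle, and only barred doses are skipped.* The last dose is then the latest scheduled dose at least 4 days before Visit 1a.

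| Schedule | Day -4 | Day -5 | Day -6 | Day -7 | Share classed *No* |
|---|---|---|---|---|---|
| Every 3 days | 1/3 | 1/3 | 1/3 | – | 1/3 = 33% |
| Alternating 3 and 4 days | 2/7 | 2/7 | 2/7 | 1/7 | 2/7 + 1/7 = 3/7 = 43% |
| Every 4 days | 1/4 | 1/4 | 1/4 | 1/4 | 1/4 + 1/4 = 1/2 = 50% |

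3. *Prophylaxis stops earlier in screening.* The share exceeds the values in the table, by an amount the documents do not allow one to fix.

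If the subgroup is the stratum itself, the share is 0% by construction.

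**Effect on the primary estimate**

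The primary analysis uses the two crossover sequences, in which a subject who completes both periods supplies a treatment contrast from within that subject. Prophylaxis status is constant within subject, so how it is coded has almost no bearing on that contrast. The 5-day rule is in any case not written into SAP 10.1 or 10.4.

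**The case against.** The strongest reply is that nothing forces the misclassification. Exclusion criterion 4 leaves Days -4 and -5 open, and a user on a 4-day interval whose next dose falls due at Visit 1a has a last dose on Day -4 and stays *Yes*. That is right. A reader might infer that the C1 INH-free interval necessarily moves stratum members to *No*. The documents support only that it can happen.

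A reader might also count 18 permitted last-dose days (Day -21 to Day -4), note that only 2 give *Yes*, and conclude that most users (16/18 = 89%) are lost. That treats a 21-day maximum as a uniform spread. Nothing in the protocol tells users to stop at consent.

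Next, SAP 12.5.6 already has a C1 INH prophylaxis level under long-term prevention at randomization, without a window and for the same endpoints. SAP 12.5.5 groups by C1 INH or androgen use before screening, for the primary endpoint only. Both reduce what is lost. Neither corrects 12.5.4, and 12.5.5 pools C1 INH with androgens.

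Finally, SAP 12.5.4 is titled as status at randomization and does not claim to be the stratum. But the plan then holds several versions of one characteristic, with no rule for a subject whose versions disagree.

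The exploratory status of the subgroups limits the seriousness of the point. It does not remove the mismatch.

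**Conclusion.** The mismatch stands. As written, SAP 12.5.4 may class as non-users some subjects randomized as C1 INH prophylaxis users, according to the timing of the last dose. The share is 0% in the most favourable case and 33% to 50% under random visit timing with only barred doses skipped. It is larger with earlier stopping. These figures rest on the stated assumptions and on enrollment meaning the Screening Visit, as Protocol 7.2.1 indicates.

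The reach is limited to exploratory subgroup results for the primary endpoint, key secondary endpoint 1 and adverse events. No confirmatory conclusion depends on them.

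A reader might infer that the 5-day window also contaminates the model covariate. The documents do not support that: the window appears only in SAP 12.5.4. What does hold for the covariate is narrower. The SAP derives it from status at randomization, the protocol names the stratification factor, and SAP 16 records no change. The expected effect on the primary estimate is negligible.

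**What to change.** 1. In SAP 12.5.4, delete the 5-day definition and define the subgroup by the randomization stratum: C1 INH prophylaxis at enrollment, yes or no.
2. Add a listing of subjects whose stratum and CRF-recorded prophylaxis disagree.
3. In SAP 10.1 and 10.4, fit that same stratum as the fixed effect, as Protocol 9.8.1 states. If the sponsor prefers the derived variable, record the departure in SAP 16.

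The cost is SAP wording and one listing. No new data are needed: the stratum is what the IRT schedule was built on, and Protocol 5.1 already collects HAE therapy over the previous 12 months, with dates if known, and all medication in the week before Day 1. Exclusion criterion 4 does not need to change.

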12.5.5 Use of Prophylactic Therapy with C1 INH or Androgens Prior to Screening

Subgroup analyses will be conducted by prophylactic therapy with C1 INH or androgens prior to screening for the primary endpoint only.

- Use of prophylactic therapy with C1 INH or androgens prior to screening: Yes
- Use of prophylactic therapy with C1 INH or androgens prior to screening: No

12.5.6 Long-Term Prevention at Randomization

Subgroup analyses will be conducted by long-term prevention at randomization.

- Any long-term prevention
- C1 INH prophylaxis
- Oral Androgen
- Oral other
- No long-term prevention

12.5.7 Region

Subgroup analyses will be conducted by region.

- North America
- Europe

12.5.8 Location

Subgroup analyses will be conducted by location.

- Upper airway (includes laryngeal or pharyngeal)
- Gastrointestinal/abdominal (including symptoms of pain, nausea, vomiting, swelling, and/or change in bowel habits)

Shire SHP616-300 Statistical Analysis Plan idursulfase IT

- Genitourinary (including scrotum or vulva)
- Cutaneous (facial)
- Cutaneous (extremity, peripheral, or torso [eg, buttocks, external head/neck, trunk])
- Non upper airway

12.5.9 Mucosal and Non-Mucosal Location

Subgroup analyses will be conducted by mucosal and non-mucosal location.

- Mucosal
- Non-mucosal
- Both mucosal and non-mucosal

Shire SHP616-300 Statistical Analysis Plan idursulfase IT Page 44

13. INTERIM ANALYSIS

There is no planned interim analysis in this study.

17 Aug 2017

14. DATA MONITORING/REVIEW COMMITTEE

There is no planned data monitoring committee in this study.

15. COMPUTER METHODS

All statistical analyses will be performed using SAS[®] Version 9.2 or higher (SAS Institute, PPD), on a suitably qualified environment.

17 Aug 2017

16. CHANGES TO ANALYSES SPECIFIED IN PROTOCOL

Not applicable.

17. DATA HANDLING CONVENTIONS

17.1 General Data Reporting Conventions

Continuous variables will be summarized using the following descriptive statistics: n, mean, SD, median, minimum, and maximum. Categorical and count variables will be summarized by the number of subjects (n) and the percent of subjects in each category.

Unless specified otherwise, min/max will be presented to the same decimal places as the raw data. Percentage, mean and median will be presented to 1 more decimal places than the raw data. Standard deviation and standard error will be presented to 2 more decimal places than the raw data.

In addition, *p*-values will generally be presented to 4 decimal places; values less than 0.0001 will be presented as <0.0001.

Treatment Columns Displayed in Summary Tables

The treatment columns displayed will differ between summary tables. Tables that summarize information only from the prior treatment or post-treatment periods will generally have the following treatment columns displayed:

Sequence A/B

Sequence B/A

Sequence A/A

Total

Tables that summarize efficacy and safety information only from the treatment period will generally have the following treatment columns displayed:

Treatment A: 2000 IU C1 INH

Treatment B: Placebo

Total (if needed)

Tables that summarize efficacy and safety information from the treatment period and treatment sequence will generally have the following treatment columns displayed:

Sequence A/B: Period 1: 2000 IU C1 INH

Sequence A/B: Period 2: Placebo

Sequence B/A: Period 1: Placebo

Sequence B/A: Period 2: 2000 IU C1 INH

Sequence A/A: Period 1: 2000 IU C1 INH

Sequence A/A: Period 2: 2000 IU C1 INH

Tables that summarize efficacy and safety information from the treatment period with different treatment sequence combinations will generally have the following treatment columns displayed:

Treatment A from Sequence A/B and B/A: 2000 IU C1 INH

Treatment A from Sequence A/A: 2000 IU C1 INH

Treatment A Overall: 2000 IU C1 INH

Treatment B: Placebo

17.2 Derived Efficacy Variables

Details on normalized efficacy variables: cumulative attack severity, cumulative daily severity, number of attack-free days, number of angioedema attacks requiring acute treatment and 98-day AAS are provided in the Appendix.

17.3 Repeated or Unscheduled Assessments of Efficacy and Safety Parameters

If a subject has repeated assessments before the date and time of the first dose of investigational product, then last assessment prior to or on the date and time of the first dose of treatment period 1 will be used as baseline. If clinical discharge assessments are repeated or unscheduled, the last assessment will be used as the clinical discharge assessment for generating descriptive statistics. However, all post-baseline assessments will be used for post-baseline overall PCI value determination, and all assessments will be presented in the data listings.

For repeated and/or unscheduled assessments, the assessment that is following the rules in the next section will be used for efficacy and safety analysis. However, all visit data (including repeated and unscheduled) will be included in subject data listings.

17.4 Termination visits for patients who discontinued investigational product or study early

For assessments collected by visits (laboratory parameters, ECG variables, vital signs parameters, scheduled questionnaire, etc), the nominal visits (CRF visits) will be used in the by-visit summaries. Only laboratory data from available visits for these assessments will be used in the analysis according to the following order:

- First, if the scheduled visit assessments exist, they will be used in the analysis;
- Second, if the scheduled visit assessments do not exist but the remapped visit assessments from TERMINATION visit exist, these assessments will be used in the analysis;
- Third, if both the scheduled visit assessments and the remapped visit assessments from termination visit do not exist but unscheduled visit assessments exist, then these assessments will be used in the analysis.

The termination visits for patients who discontinue the investigational product prematurely, are not time point specific visits. In addition to serve as the last on study assessment, they will also be remapped to nominal visits based on the following rules:

- If these visits fall into a specific visit window and the corresponding scheduled visit is missing, then these visits will be remapped to be that scheduled visit. The visit windows are defined relative to study day (if visit exists) or target day (if visit does not exist) as follows
 - ± 3 days for visits that occur every week
 - \pm 7 days for visits that occur every other week
 - ± 14 days for monthly visits
 - ± 45 days for all quarterly visits

17.5 Missing Date of Investigational Product

If the date of the last dose of investigational product is missing for a subject in the Safety Set, all efforts should be made to obtain the date from the investigator. If it is still missing after all efforts, then the last visit date when investigational product was returned will be used in the calculation of treatment duration.

17.6 Missing Date Information for Prior and Concomitant Medications

For prior and concomitant medications, incomplete (i.e., partially missing) start dates and/or stop dates will be imputed. When the start date and the stop date are both incomplete for a subject, the start date will be imputed first.

